Cigarette smokers (n=30 completers) will be recruited from advertisements through a variety of media outlets, flyers and the internet. Interested cigarette smokers will contact the University of Minnesota Tobacco Research Programs, be informed about the study and initially screened for eligibility over the telephone or HIPAA compliant website. Subjects who pass initial screening will then be asked to attend a screening visit during which the study will be explained in detail, informed consent will be obtained and the screening questionnaires and procedures will be completed to confirm eligibility. Screening procedures include: Tobacco Use History and Exposure; Fagerstrom Test for Nicotine Dependence (FTND);¹⁰⁵ Wisconsin Index of Smoking Dependence Motives¹⁴⁶; Demographics; Medical History and Current Health Status; Concomitant Medications Questionnaire; Prime MD;¹⁰⁶ Centers for Epidemiological Studies 20-item scale (CES-D);¹⁰⁷ Michigan Alcohol Screening Test (MAST) Short form;¹⁰⁸ Drug Abuse Screening Test (DAST).¹⁰⁹

Eligible participants will be asked to attend a baseline visit in the clinic. Blood pressure and heart rate will be assessed. Confirmation of smoking status will be done using a portable CO device and or a urine sample (NicCheck strip). A urine sample will also be collected to determine pregnancy status for women of childbearing potential. At the end of the baseline visit we will train participants on how to use our Interactive Voice Response System (IVRS). Participants will undergo one week of baseline measurement. Daily surveys will be completed in the IVR to assess frequency of cigarette smoking and other tobacco and marijuana use. This will provide an accurate assessment of whether or not our participants meet the eligibility criteria for smoking and an assessment of potential confounding factors. At the end of this one-week period, participants will be asked to attend 4-half day long laboratory sessions, during which 2 cigarettes (fixed puffing pattern and then *ad libitum*) will be smoked and assessments will be made (Figure 2). Daily IVR surveys will continue until the end of the study.

MEDICAL PROTOCOL (HRP-590)

PROTOCOL TITLE: Sugars Project

VERSION DATE: 22 FEB 2023

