The first session for all participants will involve smoking their UB cigarettes. Participants will be asked to refrain from smoking for at least 12 hours prior to each session and must have alveolar CO ≤ 10 ppm to qualify for the session. Subsequently, the IVR records will be examined and vitals (blood pressure and heart rate) will be assessed through an automated cuff to ensure that eligibility criteria are still met. After a 30-minute rest period, participants will complete the MNWS, submit an alveolar CO sample, and will smoke their UB cigarettes in a regimented manner (10 puffs total, 30 seconds between puffs). Five minutes after extinguishing the cigarette, another CO measurement will be taken and participants will be asked to complete the mCEQ, Drug Effects/Liking Questionnaire, MNWS, QSU and Sensory Effects of Smoking Questionnaire, in a specified order via REDCap. The spent cigarette filter will be collected for nicotine analysis. There will be a one- hour interval since the time of cigarette extinction before smoking the next cigarette. During the intervening times between cigarettes, smokers will be allowed to read magazines, listen to neutral podcasts, or watch neutral videos. After this interval, participants will submit another CO, complete the MNWS and smoke their UB cigarettes *ad libitum* within a 10-minute timeframe and the same testing procedures will be followed. Twenty minutes after the second cigarette, the Perceived Health Risk Questionnaire will be administered and then at 30 minutes the Cigarette Purchase Task and Multiple Choice Procedures for the UB cigarettes will be administered. At 50 minutes (2 hours after smoking the first cigarette), participants will be asked to rinse their mouths and oral cells will be collected. At the very end of the session, the Willingness to Switch questionnaire will be administered. Once the Willingness to Switch questionnaire has been completed a number will randomly be selected from the Multiple Choice Procedures task. This will be done by pulling a number 1- 16 out of a jar. The participants will receive either an additional cigarette or the money associated with that number, depending on which choice was made for that number. The participant may choose to smoke the cigarette or not.

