8.0 Study Population**8.1 Inclusion Criteria:**

- a) Male or female age 21 years or older;
- b) Must smoke at least 5 cigarettes/day for at least 1 year (confirmed by CO >10 ppm or NicCheck test of 6 or greater);

MEDICAL PROTOCOL (HRP-590)

PROTOCOL TITLE: Sugars Project

VERSION DATE: 22 FEB 2023

- c) Smoking cigarettes that have been evaluated to have medium levels of sugar content;
- d) No quit attempts in the past month nor intentions to quit smoking in the next month;
- e) Participants are in good physical health (no unstable medical conditions) as determined by the licensed medical professional;
- f) Participants are in stable, good mental health (e.g. not currently, within the past 6 months, experiencing unstable or untreated psychiatric diagnosis) as determined by the licensed medical professional;
- g) Stable vitals sign measurements (systolic BP \leq 160 and >90 mmHg, diastolic BP \leq 100 and >50 mmHg and heart rate \leq 105 and >45 bpm) as determined by the licensed medical professional
 - a. Participants failing for vital signs will be allowed to re-screen once;
- h) Participants must be able to read for comprehension or completion of study documents (confirmed during informed consent process);
- i) Participants have provided written informed consent to participate in the study.

8.2 Exclusion Criteria:

- a) Significant immune system disorders, respiratory diseases, kidney or liver diseases or any other medical disorders that may affect biomarker data as determined by the licensed medical professional;
- b) Current or recent alcohol or drug abuse problems or use of substances of abuse (other than marijuana) in the past month;
- c) Tobacco use other than cigarettes or marijuana for >9 days per month
- d) Current use (within past 2 weeks) of nicotine replacement or other tobacco cessation products;
- e) Women who are pregnant or nursing or planning to become pregnant.
- f) Frequent marijuana use. Quantified as >9 days of marijuana use in the last 30 days

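### The 12-hour pre-session rule covers smoking only and is tested only by CO, so recent use of non-combusted nicotine, which entry permits, can go unnoticed and add modest noise, mainly to satisfaction ratings

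*Combined protocol and SAP*

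**What the plan says.** Section 5.1 (Study Design) sets the pre-session state: "Participants will be asked to refrain from smoking for at least 12 hours prior to each session", and participants "must have alveolar CO ≤ 10 ppm to qualify for the session". The same procedures apply to the usual-brand session and the three study-cigarette sessions.

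CO is not the only thing looked at on arrival. The section continues: "Subsequently, the IVR records will be examined and vitals (blood pressure and heart rate) will be assessed", the purpose being "to ensure that eligibility criteria are still met". The survey behind those records is described earlier in 5.1: "Daily surveys will be completed in the IVR to assess frequency of cigarette smoking and other tobacco and marijuana use", and "Daily IVR surveys will continue until the end of the study". The MNWS withdrawal scale is completed before each cigarette, with no qualifying value.

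On entry, exclusion 8.2(c) reads "Tobacco use other than cigarettes or marijuana for >9 days per month", so use of other tobacco on 9 days a month or fewer is allowed. Exclusion 8.2(d) bars "Current use (within past 2 weeks) of nicotine replacement or other tobacco cessation products".

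The primary outcomes (15.1) are mCEQ satisfaction and the crossover point of the Multiple Choice Procedure. The primary model (15.3) has terms for sugar condition, session and spent-filter nicotine of the first cigarette in each session, plus a test for carry-over.

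**The concern.** The 12-hour rule and the CO limit show that the protocol wants each session to begin from a comparable state of nicotine deprivation. The rule names smoking only, and its one biochemical test responds to combustion. A participant who used smokeless tobacco or an e-cigarette that morning has followed the instruction as written and can have a low CO. That participant can also pass the survey review, because for other tobacco the relevant eligibility criterion is a monthly count.

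The analysis would not recover the loss. Section 15.3 relies on the within-subject design to remove participant-level factors, but recent use can differ from one session to the next within a person. Spent-filter nicotine reflects how the study cigarette was smoked, not the nicotine present on arrival. At stake is precision: ratings given in a less deprived state add scatter to the sugar comparison, and the planned power is only just above 80%.

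**Working it through.** **1. Which check covers what**

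| Check at the session (5.1) | Detects cigarettes in the last 12 h | Detects non-combusted nicotine in the last 12 h |
|---|---|---|
| Instruction to abstain | Yes, smoking is named | Not named |
| CO limit of 10 ppm | Yes, in principle | No |
| Survey review | Daily self-report, judged against eligibility | Daily self-report, judged against the monthly limit; no time of last use, no consequence for recent use |
| Vitals | Judged against eligibility | Judged against eligibility |
| MNWS | Records withdrawal, no threshold | Records withdrawal, no threshold |

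The right-hand column contains no rule that would stop or mark the session.

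**2. The plan's own power figure**

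Inputs from 15.2 and 15.3: n = 30, d = 0.6, r = 0.5, two-sided alpha 0.025. For a paired comparison, dz = d / √(2(1 − r)) = 0.6 / √1 = 0.6, and the noncentrality is 0.6 × √30 = 3.29 on 29 degrees of freedom. Power is 0.816, against 0.81 in the plan. The other five rows of the table also reproduce to within one percentage point. The baseline is sound.

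**3. How often a session could be affected**

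This is an illustration, because the documents give no rate of other-tobacco use. If use days fall at random and independently, the chance that at least one of the three study sessions lands on a use day is 1 − (1 − q)³:

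- 9 days in 30 (the permitted limit): 1 − 0.7³ = 0.66
- 3 days in 30: 1 − 0.9³ = 0.27
- 1 day in 30: 0.10

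These are upper figures, since use on the calendar day is not necessarily use in the preceding 12 hours.

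**4. What it would cost in precision**

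In units of the total SD, the within-person variance under the plan is 1 − r = 0.50. Suppose (assumption) that recent use shifts the outcome by δ, independently of sugar level, on a proportion q of days. The added variance for such a user is δ² × q × (1 − q). If a share s of participants are such users, the average within-person variance is 0.50 + s × δ² × q(1 − q), and the standard error is multiplied by the square root of that over 0.50.

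With δ = 0.5 and q = 0.3, the added variance is 0.25 × 0.3 × 0.7 = 0.0525.

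| Share s | Variance | SE ratio | Power at d = 0.6 |
|---|---|---|---|
| 0 | 0.5000 | 1.000 | 0.816 |
| 10% | 0.5053 | 1.005 | 0.812 |
| 20% | 0.5105 | 1.010 | 0.807 |
| 50% | 0.5263 | 1.026 | 0.794 |
| 100% | 0.5525 | 1.051 | 0.773 |

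Doubling the assumed shift to δ = 1 gives an added variance of 0.21. Power is then about 0.78 if 20% are such users, 0.73 if half are, and 0.65 if all are.

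**5. Which outcome is exposed**

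The mCEQ is first completed five minutes after the first cigarette, when the state on arrival should matter most. The Multiple Choice Procedure comes 30 minutes after the second cigarette, which itself starts an hour after the first is put out. That is at least 60 + 30 = 90 minutes and two cigarettes after the first smoking bout begins. Nicotine on arrival is largely overlaid by then.

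**The case against.** The strongest reply is that arrival state is not left unwatched. Survey records that include other tobacco are examined at every session, 5.1 describes the surveys as also a means of assessing potential confounders, and the MNWS is taken before each cigarette. This stands in part. A reader might infer that CO is the only check made, and the documents contradict that. What is missing is a rule, or a model term, that uses this information for the hours before the session.

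Second, the crossover point follows two cigarettes, so the argument barely reaches one of the two primary outcomes. That stands, and the point is confined mainly to satisfaction after the first cigarette.

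Third, the arithmetic uses the permitted maximum of 9 days and an assumed shift, and r = 0.5 may already include ordinary day-to-day variation in state, so adding variance could double count. That also stands, and the table is best read as an upper illustration.

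Fourth, nicotine replacement in the past two weeks is already excluded at entry, and smoked products such as cigars are arguably within an instruction not to smoke and could raise CO. Agreed: the gap is essentially non-combusted nicotine.

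Finally, rescheduling has a cost in a study that expects 60 to 65% attrition. That is a fair limit on how strict the remedy should be.

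**Conclusion.** The gap is real but minor. The abstinence instruction and its one biochemical test do not cover non-combusted nicotine products whose occasional use the entry criteria allow, and no other pre-session step applies a 12-hour test to them.

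Two stronger readings are tempting and are not supported. A reader might infer that participants do rate cigarettes while nicotine-sated; the documents leave that possible but do not show that it happens or how often. A reader might also infer a bias between sugar levels. Cigarettes are blinded and order is counterbalanced, so recent use has no stated reason to fall more on one level than another. The expected result is extra scatter.

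On the illustrative assumptions (0.5 SD shift, 9 of 30 days, use independent of sugar level), the standard error rises about 1% if a fifth of participants are such users and about 5% if all are, with power moving from 0.82 to 0.81 or 0.77. Larger losses need a larger assumed shift. The true size cannot be worked out from the documents.

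**What to change.** In 5.1, extend the existing 12-hour instruction from smoking to all tobacco and nicotine products. At the session check, record the time of last use of each product type.

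Where any was used within 12 hours, reschedule inside the existing interval of at least 48 hours and at most 5 days between sessions, if that is feasible. If it is not, keep the session, flag it, and add to 15.3 a pre-specified sensitivity analysis of the primary outcomes that excludes flagged sessions. The mixed model already accepts participants with incomplete sessions, so no new method is needed.

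The cost is one sentence in the instruction, one short question set at session start and one sensitivity analysis. No assay, extra planned visit or change in sample size is involved. The downside is an occasional rescheduled session in a study that already expects high attrition, which is why keeping and flagging the session should remain available.

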15.3 Statistical Analysis

General Approach

All statistical analyses will be performed using SAS or R. All statistical tests will be two-tailed. A Bonferroni adjustment will be used to account for 2 primary endpoints ($p < 0.025$ considered significant). Analyses of the secondary endpoints will not be adjusted ($p < 0.05$ considered significant). Proper transformation such as the logarithm transformation will be used to approximate normality for the outcome variables.

Describing the Study Population

Baseline characteristics of the participants will be summarized using mean and standard deviation (SD) for continuous variables and frequency and percentage for categorical variables.

Primary Analysis

The primary data analysis method will be linear mixed models including the two within-subject factors, sugar condition (2 dummy variables for the medium and high sugar levels) and time (2 dummies for the 3rd and 4th sessions), adjusted for the nicotine levels in spent filters of the first study cigarette used in each of the laboratory sessions (under the fixed puffing pattern). The potential carry-over effect will be tested by including the previous session's condition, i.e., 2 dummies for the previous session being medium and high sugar level (Diggle et al., 2002, p150-153). Note that the usual brand's measure (collected at the 1st session) and other participant-level factors are naturally adjusted across different sugar conditions because of the within-subject design, and hence are not included in the model. However, participant-level factors will be examined for any potential moderating effect (i.e., interaction) as an exploratory analysis.

Subgroup Analysis

Subgroup analyses will be performed for female and male smokers. The analyses will follow the same approach described for the overall group. Note that this study is not powered for detecting the potential interaction of gender and sugar level, however, we will report the size and significance of the interaction together with the subgroup analysis results to provide information for understanding of the role of gender.

Missing data

Every effort will be made to limit the amount of missing data in this trial, and study participants will be incentivized to attend study sessions. We anticipate a high retention rate (>80%) because of the short period of time of this laboratory study.

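### The session CO limit is weak evidence of abstinence in smokers who entered with CO at or below 10 ppm, and the pre-smoking measures that could absorb the resulting noise are not in the primary model

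*Combined protocol and SAP*

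**What the plan says.** Section 5.1 sets the session conditions: "Participants will be asked to refrain from smoking for at least 12 hours prior to each session", and they "must have alveolar CO ≤ 10 ppm to qualify for the session". It continues: "Subsequently, the IVR records will be examined and vitals (blood pressure and heart rate) will be assessed", with the aim of checking that eligibility still holds. The measures before the first cigarette come next: "After a 30-minute rest period, participants will complete the MNWS, submit an alveolar CO sample". The three study-cigarette sessions follow the same procedures as the usual-brand session.

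Section 8.1 sets the smoking requirement for entry: "Must smoke at least 5 cigarettes/day for at least 1 year", which is "confirmed by CO >10 ppm or NicCheck test of 6 or greater". The baseline-visit text in section 5.1 also allows the CO device, the urine strip, or both.

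The primary mixed model in section 15.3 has two terms for sugar level and two for session, and is "adjusted for the nicotine levels in spent filters of the first study cigarette" of each session. A carry-over test is added. The stated reason for leaving out other variables covers the usual-brand measure and characteristics of the participant. It does not mention a state that changes from session to session.

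**The concern.** The entry and session criteria use the same CO figure from opposite sides. A smoker above 10 ppm at entry has to come down to pass the session check, so for that person the check carries information. A smoker who entered on the strip with CO at or below 10 ppm is already on the passing side. For that person a pass does not separate 12 hours of abstinence from usual smoking, and the text gives no comparison with the person's own level.

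Deprivation on arrival can then vary between sessions within one participant. The within-subject design removes stable differences between people but not this. To the extent that the outcomes respond to deprivation, the variation enters the residual error and costs power. The plan already collects two measures of the arrival state before each session's cigarette, so that cigarette's sugar level cannot have altered them. Neither is in the primary model.

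**Working it through.** **The two criteria side by side**

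- Entry (8.1): CO above 10 ppm, or a NicCheck result of 6 or greater. Either is sufficient.
- Session (5.1): CO at or below 10 ppm.
- No abstinence instruction is stated for the entry reading. A participant with entry CO at or below 10 ppm therefore met the session limit on that occasion without being asked to abstain.
- IVR (5.1): daily self-report of how often the participant smokes. Time since the last cigarette is not mentioned, and the stated use is continued eligibility.

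**Reproducing the plan's power (15.2)**

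Inputs: n = 30 completers, d = 0.6, r = 0.50, two-sided alpha 0.025.

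- Set the session variance to 1. The within-person part is 1 − r = 0.5, and the variance of a high-minus-low difference is 2 × 0.5 = 1.
- Standardised difference: dz = d/√(2(1 − r)) = 0.6/1 = 0.6.
- Noncentrality: dz × √30 = 3.286, with 29 df and critical t of 2.364.
- Power from the noncentral t is 0.816; the plan states 0.81.
- The other five scenarios also reproduce: 0.898 (0.89 stated), 0.647 (0.64), 0.754 (0.75), 0.923 (0.92) and 0.968 (0.96).

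**Cost of extra noise (assumed)**

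Let undetected smoking raise within-person variance by a fraction v, with the raw sugar difference unchanged. Then dz = 0.6/√(1 + v).

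| v | dz | Noncentrality | Power, n = 30 |
|---|---|---|---|
| 0 | 0.600 | 3.286 | 0.816 |
| 0.05 | 0.586 | 3.207 | 0.795 |
| 0.10 | 0.572 | 3.133 | 0.775 |
| 0.20 | 0.548 | 3.000 | 0.735 |

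To see what might produce such a v, let f be the share of participants affected, q the chance that one of their sessions is not abstinent, and s the resulting outcome shift in SD. Averaged over participants, v = f·q(1 − q)·s²/0.5.

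- f = 0.1, q = 0.25, s = 0.5: v = 0.1 × 0.1875 × 0.25/0.5 = 0.009, power 0.812.
- f = 0.5, q = 0.5, s = 1.0: v = 0.5 × 0.25 × 1/0.5 = 0.25, power 0.716.

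The documents give none of f, q or s.

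**Gain from the covariates (assumed)**

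Three study-cigarette sessions in 30 completers give 90 observations. Removing 30 participant means, 2 sugar terms and 2 session terms leaves 90 − 30 − 4 = 56 df. Filter nicotine takes 1 (55 df), and pre-smoking CO and MNWS take 2 more (53 df). With within-person multiple correlation ρ between the two covariates and the outcome, dz = 0.6/√(1 − ρ²).

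| Model | ρ | dz | df | Power |
|---|---|---|---|---|
| Without filter nicotine or the two covariates | – | 0.600 | 56 | 0.8342 |
| As in 15.3, without the two covariates | – | 0.600 | 55 | 0.8338 |
| With the two covariates | 0 | 0.600 | 53 | 0.8331 |
| With the two covariates | 0.2 | 0.612 | 53 | 0.849 |
| With the two covariates | 0.3 | 0.629 | 53 | 0.869 |

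If the covariates explain nothing, the loss is 0.8338 − 0.8331 = 0.0007. Filter nicotine is credited with no variance reduction here. These figures assume complete data and equal correlation between sessions.

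**The case against.** The strongest reply is that the size of the problem cannot be established. The documents do not say how many participants will enter with CO at or below 10 ppm. Entry CO is one reading on one day and does not show that the person stays below the limit whenever smoking freely. The session check still catches smoking that lifts CO above 10 ppm, and IVR records are reviewed at each session. All of this stands. A reader might infer that the check is void for this group, or met without any abstinence; the text supports only that a pass is weak evidence.

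A reader might also infer bias between sugar levels. The documents point the other way: order is counterbalanced by a Latin square and the cigarettes are blinded, so undetected smoking should be unrelated to sugar level.

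It is tempting to express the harm as r falling from 0.5 to 0.4 and to read power off at d = 0.6. That calculation gives 0.735 but does not fit the mechanism, because added noise raises the total SD and so also lowers d. Noise that brings r to 0.4 means a 50% rise in within-person variance, since 0.5/(0.5 + 0.75) = 0.4, and power would be 0.627. The figure 0.735 belongs to a 20% rise, where r is 0.5/(0.5 + 0.6) = 0.45. Further, nothing in 15.2 says that the planning value r = 0.50 excludes ordinary variation in deprivation, so part of the loss may already be counted.

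Finally, the Multiple Choice Procedure is given 30 minutes after the second cigarette. The arrival state is remote from it, and the documents give no ground for a correlation of 0.2 to 0.3 there. This also stands. The mCEQ is first completed five minutes after the first cigarette, so satisfaction is where the covariates are more likely to help.

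**Conclusion.** The point holds as a minor one about precision. The two criteria leave abstinence poorly verified in a subgroup of unknown size, and the primary model leaves out arrival measures that are already collected. The stated power is correct on its own inputs, but it has little margin: a 5% rise in within-person variance would take 0.816 to 0.795, below the 80% claimed.

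The noise levels and correlations are assumptions, and the loss may be close to nil. The covariate gain at the assumed correlations is 1.5 to 3.5 percentage points (0.834 to 0.849 or 0.869). It comes from general adjustment across all 30 participants and is not specific to those who entered on the strip. The case for the change rests on its negligible cost more than on a demonstrated harm. Whether filter nicotine, collected after smoking, is a suitable covariate is a separate question, and this conclusion does not depend on it.

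**What to change.** In section 15.3, add one sentence pre-specifying each session's MNWS score and CO reading, both taken after the rest period and before the first cigarette, as session-level covariates in the primary model. Naming the reading matters because section 5.1 also has a CO check to qualify for the session, and CO and MNWS are repeated after the first cigarette and before the second. State that the main benefit is expected for mCEQ satisfaction and less for the crossover point.

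The cost is two degrees of freedom, under 0.001 of power if the covariates explain nothing, and no new measurement.

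Separately, the study team should reconcile the entry criterion in 8.1 and the baseline-visit text in 5.1 with the session CO criterion in 5.1, and state what the session check is meant to show for participants who entered on the urine strip. A comparison with the participant's own entry CO may come to mind, but the plan gives no criterion for it, and the either-or wording means that an entry CO may not be recorded. No threshold or qualification rule is proposed here.
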